16.3. Participant Information and Consent

It is the responsibility of the investigator to obtain and document written informed consent from the participant. Informed consent in compliance with the principles of informed consent in ICH E6 and all applicable local regulations should be obtained before any protocol-specified procedures or interventions are conducted. The sponsor reserves the right to delay initiation of the study at a site where ICFs do not meet the standards of applicable local regulations or ICH E6.

Information should be given to the participant in both oral and written form, and participants must be given ample opportunity to inquire about details of the study.

The consent form generated by the investigator must be approved by the IRB/IEC. The investigator will provide the sponsor with a copy of the IRB/IEC-approved consent forms and a copy of the IRB/IEC's written approval before the start of the study.

Consent forms must be written (and appropriately translated in the participant's native language or language in which the participant has fluency) so as to be understood by the prospective participant. Informed consent will be documented by the use of a written consent form approved by the IRB/IEC. The form must be signed and dated by the participant and by the person who conducted the discussion of the informed consent.

All versions of each participant's signed ICF must be kept on file by the investigator for possible inspection by regulatory authorities and/or authorized sponsor monitoring and regulatory compliance persons. The participant should receive a copy of the signed and dated written ICF and any other written information provided to the participant.

16.4. Participant Confidentiality

To maintain confidentiality of participants, all laboratory specimens, evaluation forms, reports, and other records will be identified by a coded number. Clinical information will not be released without written permission of the participant or an individual with legal decision-making authority for the participant or the participant's interests, except as necessary for monitoring by the relevant regulatory authorities, the sponsor of the clinical study, or the sponsor's representative. The investigator must comply with all local applicable privacy regulations for protection of personal data (eg, US Health Insurance Portability and Accountability Act of 1996 or European Union General Data Protection Regulation).

16.5. Case Report Forms and Study Records

Source data in a clinical study are the original records or certified copies where clinical observations are first recorded, which may include, but are not limited to, the participant's

medical file, original laboratory reports, histology, and pathology reports (as applicable). The investigator is responsible for maintaining adequate and accurate medical records from which accurate information will be entered into the eCRFs designed to capture data pertinent to the clinical investigation. Data should be recorded on paper source documents or electronic in an electronic medical records system. The eCRFs should be completed in their entirety by the investigator or their designee. Prior to eCRF database lock, the investigator will verify the completeness and accuracy of the data and indicate that he/she has done so by providing an electronic signature on the appropriate eCRF. The investigator will retain a copy of all source documents.

16.6. Access to Source Documentation

The investigator and study center will permit the sponsor, its representatives, IRB/IEC, and all relevant regulatory agencies access to all original source data and documents regardless of media, for study monitoring audits and inspections.

16.7. Retention of Data

Per ICH guidelines, all essential documents, including eCRFs, source documents (regardless of media), signed ICFs, and laboratory test results, must be retained by the investigator for at least 2 years after last approval of a marketing application in an ICH region and until there are no pending or contemplated marketing applications in an ICH region or until at least 2 years have elapsed since formal discontinuation of clinical development of the investigational product. There may be other circumstances for which the sponsor is required to maintain study records for longer periods; therefore, the sponsor must be contacted before study records are removed from the control of the study site for any reason. The investigator must obtain written permission from the sponsor prior to destruction of study documents.

16.8. Sample Retention and Further Testing

Samples acquired for protocol-specified assays will be retained for at least 1 year following the end of the study and may be retained up to 2 years after last approval of a marketing application in an ICH region and until there are no pending or contemplated marketing applications in an ICH region or until at least 2 years have elapsed since formal discontinuation of clinical development of the investigational product. If the participant consents, or an individual with legal decision-making authority for the participant or the participant's interests consent, to the use of their study samples for non-study research purposes, these samples may also be used for exploratory testing (including assay development/optimization) and may be retained up to 15 years from the end of the study.

16.9. Financial Disclosure

The investigator and sub-investigators will be required to disclose any applicable financial arrangement as defined in US regulations (ie, 21 CFR 54).

The following information will be collected about the investigators, their spouse, and each dependent child: any significant payments of other sorts from sponsor, or any alliance partner, such as a grant to fund ongoing research, compensation in the form of equipment, retainer for

ongoing consultation or honoraria; any proprietary interest in the study drug; and any significant equity interest in sponsor, as defined in 21 CFR 54. Investigators are obliged to update the sponsor with any changes in reported information up to 1 year following the end of the study.

Investigators and sub-investigators will be required to disclose if they are an employee of the sponsor, or an immediate family member of a sponsor employee, officer, or director. This is to assist the sponsor with its compliance with Securities and Exchange Commission rules requiring disclosure of certain transactions with related persons as defined in 17 CFR 229.404. "Immediate family member of a sponsor employee" means a child, stepchild, parent, stepparent, spouse, sibling, mother-in-law, father-in-law, son-in-law, brother-in-law, or sister-in-law of any sponsor employee, officer, or director or any person sharing the household of such sponsor employee, officer, or director.

In consideration of participation in the study, the sponsor will pay the investigator or nominated payee the sums set out in the payment schedule attached to the investigator agreement.

Financial disclosure information will be documented in writing and signed and dated by the investigator. This information will be collected prior to that investigator taking part in the research.

16.10. Publication and Disclosure Policy

Data collected in this clinical study belong to the sponsor. The publication terms regarding use of the study data will be noted in the clinical trial agreement. This includes authorship: scheduling and prioritizing analyses for reports, publications, and presentations; and developing a review and approval process.

16.11. Discontinuation of the Study or Study Sites

16.11.1. Discontinuation of Study Sites

Site participation may be discontinued if the sponsor, the investigator, a regulatory authority, or the IRB/IEC of the study sites deems it necessary for any reason.

16.11.2. Discontinuation of the Study

The study may be discontinued by a regulatory authority or at the discretion of the sponsor. Changes in the risk/benefit profile will prompt a review of the study in conjunction with the local regulatory authority.

The investigator maintains the right to discontinue their participation in the study should their clinical judgment so dictate. The investigator will notify the IRB/IEC of any study discontinuation. Study records must be retained as noted above.

16.12. Identification of the Coordinating Principal Investigator

A coordinating principal investigator will be appointed by the sponsor prior to the end of the study.

As part of his or her responsibilities, the coordinating principal investigator will review the final clinical study report. Agreement with the final clinical study report will be documented by the dated signature of the coordinating principal investigator.

18. APPENDICES

APPENDIX 1. TIME AND EVENTS SCHEDULE (SCHEDULE A - 21 DAY CYCLE)

	g .			Cycle 1				≥ Cycle 2	2		
EVALUATION/ PROCEDURE	Screening (within 28 days)	Day 1	Day 2	Day 3 (+ 1d)	Day 8 (± 1d)	Day 15 (± 1d)	Day 1 (+ 3d)	Day 8 (± 1d)	Day 15 (± 1d)	EOTV	Follow-up
Informed consent	X										
Eligibility criteria review	X										
Medical/cancer history	X										
Tumor specimen ^a	X										
Physical examination ^b	X	X			X	X	X	X	X	X	
Concomitant medications/procedures			•	(Continuous	S	•	•	•	X	
ECOG performance status-c	X	X					X			X	
12-lead ECG ^d	X	X			X		X			X	
Echocardiogram/MUGA ^e	X									X	
Ophthalmic examination ^f	X				etc.). Par	xams at the ticipants wi Table 7.				X	
Ocular symptoms assessment ^g		X			X	X	X	X	X	X	
Pregnancy test h	X	X					X			X	
Assess for AEs			•	•	•	Continuou	ıs	•	•	•	•
Vital signs i	X	X		X	X	X	X	X	X	X	
Hematology/chemistry j	X	X		X		X	X	X		X	
Coagulation ^j	X	X		X		X	X	X		X	
Endocrine ^j	X									X	
Urinalysis ^j	X	X					X			X	

	Caraanina	Cycle 1 ≥ Cycle 2						2			
EVALUATION/ PROCEDURE	Screening (within 28 days)	Day 1	Day 2	Day 3 (+ 1d)	Day 8 (± 1d)	Day 15 (± 1d)	Day 1 (+ 3d)	Day 8 (± 1d)	Day 15 (± 1d)	EOTV	Follow-up
PK/ADA/Biomarker					S	ee Append	ix 4				
Tumor markers eg, CEA or CA19-9 k	X			Q6W (±	3 days) st	arting Cycl	e 1 Day 1	k		X	
Disease assessment	X		Q6W (±	7 days) w	hile on stu	dy drug the	en Q12W (± 21 days) 1	X¹	
Follow-up assessments m											X ^m
Administer IMGC936		X					X				

Abbreviations: ADA: antidrug antibody; AE: adverse events; C: cycle; CA19-9: carbohydrate antigen 19-9; CEA: carcinoembryonic antigen; D/d: day; ECG: electrocardiography; ECOG: Eastern Cooperative Oncology Group; EOI: end of infusion; EOTV: end of treatment visit; LTFU: lost to follow-up; LVEF: left ventricular ejection fraction; MUGA, multigated acquisition scan; PD: progressive disease; PK: pharmacokinetic; QxW: every x weeks; RECIST: Response Evaluation Criteria in Solid Tumors; RP2D: recommended Phase 2 dose.

- ^a All participants to be enrolled in the study must have an identified formalin-fixed, paraffin embedded tumor specimen or slides as detailed in the laboratory manual; see Section 9.13. Participants may undergo a low-risk, medically routine procedure to obtain a specimen for testing if a suitable archival sample cannot be identified. The specimens will be analyzed retrospectively and will not be used to determine eligibility.
- b Includes height (screening only) and weight. Weight may be obtained within 24 hours of Cycle 1 Day 1. Full physical examinations are performed at screening, Cycle 1 Day 1 (or within 24 hours before the first infusion), and EOTV. All other physical examinations are directed physical examinations based on symptoms, tumor location, and as clinically indicated. Participants in dose escalation cohorts will have weekly directed physical examination through treatment Cycle 3. Beginning on Cycle 4, physical examination is only required on Day 1 of each cycle. Participants in the dose expansion cohorts should have physical examination recorded on Day 1 of each treatment cycle.
- ^c ECOG performance status should be the primary performance measure for participant enrollment. If ECOG performance status is an inappropriate performance measurement for participant enrollment (eg, chronically nonambulatory), then Karnofsky performance status may be used. A description of the scale is in Appendix 8. ECOG assessment at C1D1 can be performed within 24 hours before the infusion.
- d On Day 1 of Cycle 1, 2 and 3, ECGs are recorded pre-infusion (within 30 minutes before) and EOI (within 30 minutes after EOI). During selected non-dosing visits (eg, screening, C1D8, and EOTV), ECGs will be recorded.
- ^e The Investigator to choose appropriate modality (eg, echocardiogram or MUGA) to assess LVEF.
- ophthalmic examinations are performed at screening by an ophthalmologist per Section 9.12. All participants will have a complete ophthalmological examination when ocular symptoms and signs develop, repeated per Table 7. Participants without ocular symptoms or signs should have an ophthalmic examination at the end of Cycle 2, followed with ophthalmic exams every 3 cycles/ 9 weeks (at the end of Cycle 5,8, etc.) in both dose escalation and expansion phases. Participants with Grade 2 or greater ocular AEs which have not resolved to Grade 1 or baseline must have an ophthalmic examination at EOTV. All other participants are recommended to have an ophthalmic examination at EOTV to document any subclinical findings.
- ^g Ocular symptom assessment at C1D1 can be performed within 24 hours before the infusion. For participants in dose escalation cohorts, ocular symptoms assessment should occur weekly during the first 3 cycles and subsequently Day 1 of each cycle. During the Dose Expansion Phase (at RP2D), if limited ocular

toxicity is observed during escalation, ocular symptom assessment will occur on Day 1 of each cycle or more frequently if ocular symptoms and signs are observed. Phone-based ocular symptom assessments are acceptable if no clinic visit is scheduled.

- ^h Females of childbearing potential only. Serum pregnancy test is required for eligibility. Subsequent pregnancy tests may use serum or urine. Results must be reviewed before study drug infusion on Day 1 of Cycle 1 and all subsequent cycles. If screening test is performed within 72 hours of first infusion, repeat of the test on Day 1 may be deferred.
- During non-dosing visits (eg, screening and EOTV), vital signs will be taken at one timepoint. For Cycle 1 Day 1, vitals are measured pre-infusion (within 30 minutes before); 15 and 30 minutes after start of infusion (± 5 minutes); EOI (± 10 minutes); and 2, 4, and 6 hours after EOI (± 10 minutes). For Cycle 2 Day 1 and subsequent cycles, vitals are measured pre-infusion (within 30 minutes before), EOI (± 10 minutes), and 1 hour after EOI (± 10 minutes). Participants in dose escalation cohorts must have vital signs recorded on both dosing and non-dosing days through treatment Cycle 3. Beginning on Cycle 4, vital signs must be recorded on Day 1 of each treatment cycle. Participants in expansion cohorts must have vital signs recorded on Day 1 of each treatment cycle.
- ^j To be obtained pre-infusion. Day 1 laboratory samples can be obtained up to 3 days before infusion. Chemistry and hematology results must be reviewed before study drug administration. See Appendix 3 for assessments. Beginning on Cycle 4, laboratory samples only required on Day 1 of each cycle.
- ^k Tumor markers are obtained as indicated for each specific tumor type, eg, CEA for colorectal cancer and CA19-9 for pancreatic cancer. Repeat collection on Cycle 1 Day 1 if screening collection > 7 days prior.
- Tumor assessments are Q6W (\pm 7 days) while participant is on study drug, then Q12W (\pm 21 days). Assessments continue until discontinuation criteria are met. Tumor assessments are performed at EOTV except if prior assessment was \leq 30 days of EOTV and results are available for RECIST v1.1 assessment.
- ^m Tumor assessments will occur after participant has discontinued study drug Q12W (± 21 days) until evidence of PD, initiation of another anticancer therapy, withdrawal of consent, LTFU, death, or end of study, whichever occurs first.

APPENDIX 2. TIME AND EVENTS SCHEDULE (SCHEDULE B - 28 DAY CYCLE)

	I	1								l				
					Cycle 1	and Cyc	ele 2				≥Cycle :	3		
EVALUATION/ PROCEDURE	Screen- ing (within 28 d)	Day 1	Day 2	Day 3 (+ 1d)	Day 8 (± 1d)	Day 15 (± 1d)	Day 16 (± 1d) (Cycle 1 PK only)	Day 17 (±1d) (Cycle 1 PK only)	Day 22 (± 1d)	Day 1 (±3d)	Day 8 (±1d)	Day 15 (±1d) (Cycle 3 only)	EOTV	Follow -up
Informed consent	X													
Eligibility criteria review	X													
Medical/ cancer history	X													
Tumor specimen ^a	X													
Physical examination b	X	X			X	X			X	X	X	X	X	
Concomitant medications/ procedures		•				Cor	ntinuous						X	
ECOG performance status-c	X	X		X	X	X			X	X	X		X	
12-lead ECG ^d	X	X			X	X				X			X	
Echocardiogram/MUGA e	X													
Ophthalmic examination ^f	X	Asy	mptoma				ne end of Coular sympt					5, 8, 11,	X	
Ocular Symptoms Assessment ^g		X			X	X			X	X	X	X	X	
Pregnancy test h	X	X			X	X				X	X		X	
Assess for AEs		•		•			Cont	inuous	•	•	•	•	•	
Vital signs i	X	X		X	X	X			X	X	X	X	X	
Hematology/chemistry j	X	X		X	X	X			X	X	X	X	X	
Coagulation ^j	X	X		X	X	X			X	X	X	X	X	

					Cycle 1	and Cyc	ele 2				≥Cycle .	3		
EVALUATION/ PROCEDURE	Screening (within 28 d)	Day 1	Day 2	Day 3 (+ 1d)	Day 8 (± 1d)	Day 15 (± 1d)	Day 16 (± 1d) (Cycle 1 PK only)	Day 17 (±1d) (Cycle 1 PK only)	Day 22 (± 1d)	Day 1 (±3d)	Day 8 (±1d)	Day 15 (±1d) (Cycle 3 only)	EOTV	Follow -up
Endocrine ^j	X													
Urinalysis ^j	X	X								X				
PK/ADA/Biomarker							See Ap	pendix 5						
Tumor markers eg, CEA or CA19-9 k	X				Q8	W (± 3 da	ıys) startinş	g Cycle 1 l	Day 1 ^k				X	
Disease assessment	X			Q8V	V (± 7 day	(s) while	on study dr	ug then Q	12W (± 21	days)1			X¹	
Follow-up assessments ^m														X m
Administer IMGC936		X			X	Xn				X	X			

Abbreviations: ADA: antidrug antibody; AE: adverse events; C: Cycle; CA19-9: carbohydrate antigen 19-9; CEA: carcinoembryonic antigen; D/d: day; ECG: electrocardiography; ECOG: Eastern Cooperative Oncology Group; EOI: end of infusion; EOTV: end of treatment visit; LTFU: lost to follow-up; LVEF: left ventricular ejection fraction; MUGA, multigated acquisition scan; PD: progressive disease; PK: pharmacokinetic; QxW: every x weeks; RECIST: Response Evaluation Criteria in Solid Tumors; RP2D: recommended Phase 2 dose.

- ^a All participants to be enrolled in the study must have an identified formalin-fixed, paraffin embedded tumor specimen or slides as detailed in the laboratory manual; see Section 9.13. Participants may undergo a fresh tumor biopsy using a low-risk, medically routine procedure to obtain a specimen for testing if a suitable sample cannot be identified. The specimens will be analyzed retrospectively and will not be used to determine eligibility.
- b Includes height (screening only) and weight. Weight may be obtained within 24 hours of Cycle 1 Day 1. Full physical examinations are performed at screening, Cycle 1 Day 1 (or within 24 hours before the first infusion), and EOTV. All other physical examinations are directed physical examinations based on symptoms, tumor location, and as clinically indicated. Participants in dose escalation cohorts will have weekly directed physical examination through in Cycles 1 and 2, and directed physical examinations on Cycle 3 Day 1, Day 8, and Day 15. Beginning on Cycle 4, physical examination is only required on each dosing visit of each cycle, ie, Day 1 and Day 8. Participants in the dose expansion cohorts will have a physical examination recorded on each dosing visit.
- ^c ECOG performance status should be the primary performance measure for participant enrollment. If ECOG performance status is an inappropriate performance measurement for participant enrollment (eg, chronically nonambulatory), then Karnofsky performance status may be used. A description of the scale is in Appendix 8. ECOG assessment at C1D1 can be performed within 24 hours before the infusion.
- ^d For Cycle 1 Day 1, 8, and 15, ECGs are recorded pre-infusion (within 30 minutes before) and EOI (within 30 minutes after EOI). For Cycle 2 Day 1 and Cycle 3 Day 1, ECGs are recorded pre-infusion (within 24 hours before) and at EOI (within 30 minutes after EOI). During selected non-dosing visits (eg, screening and EOTV), ECGs will be recorded.
- ^e The Investigator to choose appropriate modality (eg, echocardiogram or MUGA) to assess LVEF.

- f Ophthalmic examinations are performed at screening by an ophthalmologist per Section 9.12. All participants will have a complete ophthalmological examination when ocular symptoms or signs develop, repeated per Table 7. Participants without ocular symptoms or signs should have an ophthalmic examination at the end of Cycle 2, followed with ophthalmic examinations every 3 cycles/ 12 weeks (at the end of Cycle 5, 8, etc.) in both dose escalation and expansion phases. Participants with Grade 2 or greater ocular AEs which have not resolved to Grade 1 or baseline must have an ophthalmic examination at EOTV. All other participants are recommended to have an ophthalmic examination at EOTV to document any subclinical findings.
- g Ocular symptom assessment at C1D1 can be performed within 24 hours before the infusion. For participants in dose escalation cohorts, ocular symptoms assessment should occur weekly in Cycle 1 and 2, and occur on Day 1 and Day 8 in each subsequent cycle. Participants' ocular symptoms and signs are also evaluated on C3D15. During the Dose Expansion Phase (at RP2D), if limited ocular toxicity is observed during escalation, ocular symptom assessment will occur on Day 1 of each cycle or more frequently if ocular symptoms or signs are observed. Phone-based ocular symptom assessments are acceptable if no clinic visit is scheduled.
- ^h Females of childbearing potential only. Serum pregnancy test is required for eligibility. Subsequent pregnancy tests may use serum or urine. Results must be reviewed before study drug infusion on Day 1 of Cycle 1 and all subsequent cycles. If screening test is performed within 72 hours of first infusion, repeat of the test on Day 1 may be deferred.
- Participants in dose escalation cohorts must have vital signs recorded on both dosing and non-dosing days through treatment Cycle 3. During non-dosing visits (eg, screening and EOTV), vital signs will be taken at one timepoint. For Cycle 1 Day 1, vitals are measured pre-infusion (within 30 minutes before); 15 and 30 minutes after start of infusion (± 5 minutes); EOI (± 10 minutes); and 2, 4, and 6 hours after EOI (± 10 minutes). During other dosing visits up to Cycle 3, vitals are measured pre-infusion (within 30 minutes before), EOI (± 10 minutes), and 1 hour after EOI (± 10 minutes). Beginning on Cycle 4, vital signs must be recorded on each dosing visit. Participants in expansion cohorts must have vital signs recorded on each dosing visit.
- ^j To be obtained pre-infusion. Day 1 laboratory samples can be obtained up to 3 days before infusion. Chemistry and hematology results must be reviewed before study drug administration. See Appendix 3 for assessments.
- ^k Tumor markers are obtained as indicated for each specific tumor type, eg, CEA for colorectal cancer and CA19-9 for pancreatic cancer. Repeat collection on Cycle 1 Day 1 if screening collection > 7 days prior.
- ¹ Tumor assessments are Q8W (± 7 days) while participant is on study drug, then Q12W (± 21 days). Assessments continue until discontinuation criteria are met. Tumor assessments are performed at EOTV except if prior assessment was ≤ 30 days of EOTV and results are available for RECIST v1.1 assessment.
- ^m Tumor assessments will occur after participant has discontinued study drug Q12W (± 21 days) until evidence of PD, initiation of another anticancer therapy, withdrawal of consent, LTFU, death, or end of study, whichever occurs first.
- ⁿ Day 15 dose may be omitted in Cycle 2 if significant ocular events occurred in Cycle 1, at the discretion of the investigator.

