6. STUDY DRUG ADMINISTRATION

6.1. Description of Study Drug Administration

IMGC936 is administered by IV infusion. The drug product is diluted in a solution of sterile Dextrose 5% in Water (D5W) in an IV bag for administration with an infusion pump.

For Schedule A, IMGC936 is administered on Day 1 of each 21-day cycle.

For Schedule B, IMGC936 is administered on Day 1, Day 8, and Day 15 of a 28-day cycle for Cycles 1 and 2. For each subsequent 28-day cycle (Cycle 3 and beyond), IMGC936 is administered on Day 1 and Day 8. Subsequent cycles may be delayed up to 3 days after the previous cycle for scheduling purposes. IMGC936 is administered as an IV infusion at the assigned dose for each cohort, over approximately 2 to 3 hours.

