7.2. Ocular Toxicity

Maytansinoids are known to cause ocular toxicity when used as the payload in ADCs. IMGC936-related ophthalmic findings were observed in repeat-dose nonclinical studies. These findings included reversible ocular events, eg, discharge, conjunctival swelling, congestion and/or cloudiness, pannus, cellular or keratic precipitates, and corneal pigmentation in one or both eyes and microscopic changes of minimal to moderate single cell necrosis and minimal to mild increased mitoses.

Ocular events have been observed in patients receiving IMGC936 in clinical trials. As such, participants should be monitored for symptoms with each cycle and action taken as noted below both to monitor for and manage ocular toxicity should it arise. Ocular symptoms and signs to be closely monitored are included but not limited to those defined in the IMGC936 Investigator's Brochure, Section 6.6.2.

For participants in dose escalation cohorts in Schedule A, ocular symptom assessment should occur weekly during the first 3 cycles and subsequently on Day 1 of each cycle. For participants in dose escalation cohorts in Schedule B, ocular symptom assessment should occur weekly in Cycle 1 and 2, and occur on Day 1 and Day 8 in each subsequent cycle. Participants' ocular symptoms and signs are also evaluated on Cycle 3 Day 15.

During the Dose Expansion Phase (at the RP2D), if ocular toxicity is limited (eg, does not lead to dose reductions or discontinuations in > 10% of participants) at the RP2D during escalation, ocular symptom assessment will occur on Day 1 of each cycle or more frequently if ocular symptoms or signs are observed. Phone-based ocular symptoms assessments are acceptable if no clinic visit is scheduled. If a participant develops ocular symptoms or signs of any grade (eg, blurred vision, dry eye, eye pain), the participant is required to have a complete ophthalmic examination by an ophthalmologist. If a participant develops ≥ Grade 2 ocular symptoms or signs, the study drug must be interrupted. Study drug may resume if ocular symptoms or signs improve to Grade 1 or baseline within 14 days (see Table 7 for details). Subsequent ophthalmic examinations will be scheduled to occur in every other cycle going forward, from the time that the AE was initially reported until resolution to Grade 1 or less, stabilization, or return to baseline, even after study drug discontinuation, if needed.

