9.6. Physical Examination

The investigator will perform physical examination of all participants per the schedule in Appendix 1 and Appendix 2. A full physical examination includes height (screening only), weight, and examination of head, eyes, ears, nose, throat, lymph nodes, heart, chest, lungs, abdomen, extremities, neurologic system, and skin examination.

Directed physical examination will be conducted per Appendix 1 and Appendix 2. The examination will be based on review of participant symptoms, medical history, and as clinically indicated. Each examination will include a total body skin examination to detect mucocutaneous AEs. Participants on Schedule A in dose escalation cohorts will have weekly directed physical examination through treatment Cycle 3. Beginning on Cycle 4, physical examination will occur on Day 1 of each cycle (Schedule A). Participants on Schedule B in dose escalation cohorts will have weekly directed physical examination in Cycle 1 and 2, and directed physical examination on Cycle 3 Day 1, Day 8, and Day 15. Beginning on Cycle 4, physical examination will occur on each dosing visit of each cycle (Schedule B).

Participants in the dose expansion cohorts will have physical examination recorded on Day 1 of each treatment cycle (Schedule A) or each dosing visit (Schedule B).

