Ocular symptoms and signs assessment will be performed by the treating physician or other qualified individual. For participants reporting > Grade 1 ocular symptoms and signs, treatment will be held until the participant is evaluated by an ophthalmologist for a complete examination (Section 7.2).

Participants in the ocular sub-study will be monitored for the frequency and severity of ocular events as usual. Participants without ocular symptoms or signs should have an ophthalmic examination at the end of Cycle 2 and followed with ophthalmic examinations every three cycles until the end of treatment. Participants with ocular AEs must have ophthalmological examinations per Table 7, but will be required to have an early ocular examination after 2 cycles of therapy (instead of after 3 cycles) regardless of whether they have ocular symptoms and signs.

9.13. **Archival Tumor Tissue**

Participants must submit archival tumor tissue (FFPE block, or unstained slides) for analysis of ADAM9 expression. If a participant does not have archival material available for analysis, the participant may alternatively undergo a low-risk, medically routine procedure to obtain a tissue sample, if appropriate. The decision to biopsy will be made once participant eligibility has been determined and on the basis of tumor accessibility and participant safety. This will typically require that the tumor lesions are superficially accessible or that the lesions can be biopsied under CT or ultrasound guidance without traversing major blood vessels or other vital structures. The specimens will be analyzed retrospectively and will not be used to determine participant

eligibility. Instructions regarding processing and shipment of archival tissues and biopsy samples are detailed in the Laboratory Manual.

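### In Schedule B expansion at the RP2D, the reduced ocular symptom check falls only on Day 1 of each cycle, so no check is required before the Day 8 and Day 15 infusions

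*Protocol*

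**What the plan says.** Schedule B dosing is set in Protocol Section 6.1: "IMGC936 is administered on Day 1, Day 8, and Day 15 of a 28-day cycle for Cycles 1 and 2". From Cycle 3 the infusions are on Days 1 and 8. Section 4.1.2 lets the sponsor place any of expansion Cohorts A to G on either schedule.

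The Appendix 2 grid has a row for "Ocular Symptoms Assessment ^g", marked on every Schedule B dosing day. Footnote g qualifies that row. Escalation cohorts are assessed weekly in Cycles 1 and 2 and on Days 1 and 8 afterwards. For expansion it reads: "Dose Expansion Phase (at RP2D), if limited ocular toxicity is observed during escalation, ocular symptom assessment will occur on Day 1 of each cycle". Section 7.2 states the same rule without separating the schedules: "ocular symptom assessment will occur on Day 1 of each cycle or more frequently if ocular symptoms or signs are observed". As an example of limited toxicity, Section 7.2 offers ocular events causing dose reduction or discontinuation in no more than 10% of participants at the RP2D in escalation.

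Two rules act on what is found. Section 7.2 says that at or above "Grade 2 ocular symptoms or signs, the study drug must be interrupted". Section 9.12 adds: "For participants reporting > Grade 1 ocular symptoms and signs, treatment will be held until the participant is evaluated by an ophthalmologist".

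For another expansion check, Appendix 2 footnote b does follow the Schedule B dosing days: "Participants in the dose expansion cohorts will have a physical examination recorded on each dosing visit". Section 9.6 makes the same split, using Day 1 for Schedule A and each dosing visit for Schedule B.

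**The concern.** A once-per-cycle ocular check covers every dose on Schedule A. On Schedule B the same wording leaves infusions uncovered. It reads like a Schedule A rule carried over unchanged, because Appendix 1 footnote g has essentially the same sentence and because physical examination was adapted to Schedule B.

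The stake is participant safety, not an endpoint or a decision rule. The dose hold works only if the symptom is known before the infusion. Under Section 9.12 it depends on the participant reporting it. Someone with no earlier ocular symptom who reaches Grade 2 after Day 1, and does not mention it at the Day 8 or Day 15 visit, could be infused when the protocol requires a hold. Ocular events are a recognised risk here: Section 7.2 says they have been seen in patients on this drug, and Section 4.1.1 gives their possible reduction as a reason for Schedule B.

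**Working it through.** No sample size, power or error rate is involved. The check sets the infusion days beside the required assessment days and counts.

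**Conditions assumed:** expansion on Schedule B, at the RP2D, escalation ocular toxicity judged limited, and no ocular symptom or sign yet observed.

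| Period | Infusion days (Section 6.1) | Required assessment days (footnote g) | Infusions without one |
|---|---|---|---|
| Cycle 1 | 1, 8, 15 | 1 | 2 |
| Cycle 2 | 1, 8, 15 | 1 | 2 |
| Each cycle from Cycle 3 | 1, 8 | 1 | 1 |

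- Cycles 1 and 2: 3 × 2 = 6 infusions and 1 × 2 = 2 assessments, so 6 − 2 = 4 of 6 infusions are uncovered.
- Each cycle from Cycle 3: 2 − 1 = 1 of 2 uncovered.
- Over six cycles: 6 + (4 × 2) = 14 infusions and 6 assessments, so 14 − 6 = 8 uncovered.
- On Schedule A the count is zero, because Day 1 is the only infusion day.

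Appendix 2 footnote n allows the Cycle 2 Day 15 dose to be omitted after significant ocular events in Cycle 1. That would give 3 of 5, but such a participant has already had an ocular event and is outside the group counted here.

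**Does anything else restore a check before the dose?**

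- *Directed physical examination at each dosing visit (Section 9.6, footnote b).* It is guided by symptoms, but no ocular question is specified. Only the full examination lists the eyes.
- *Continuous adverse event assessment.* It applies throughout, with no ocular question specified before a dose.
- *Weekly ocular assessments in Table 7.* They begin once an ocular event of any grade is known, so they do not reach a participant with none.
- *Scheduled ophthalmic examination.* Without symptoms, the first on treatment is at the end of Cycle 2, about Day 2 × 28 = 56, after all 6 infusions.

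None of these is a required ocular symptom assessment before the Day 8 or Day 15 infusion.

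**Does limited toxicity in escalation remove the need?** Not by the example in Section 7.2, which counts only dose reductions and discontinuations. Under Table 7, a Grade 2 event that resolves within 14 days may be followed by the same dose. Such an event requires a hold but would not count toward the 10%.

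**The case against.** The strongest objection is that the case may never arise. The reduced rule applies at the RP2D. SAP Section 7 gives this as 6 mg/kg, a Schedule A level in Protocol Table 2, while Table 3 for Schedule B stops at 4.0 mg/kg per dose. Schedule B expansion might then be an alternate dose and schedule under Cohort F or G, arguably outside the reduced rule and with the grid marks in force. This stands as a limit on scope. It does not remove the point, because Section 4.1.2 still allows Schedule B in any cohort, and the grid and footnote leave sites to settle which governs.

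Second, the reduction may be a deliberate response to risk. If a Schedule B dose became the RP2D, escalation data with ocular assessments on every infusion day would inform the judgement. That is a fair reason to drop non-dosing checks such as Day 22. It is weaker for dosing days, since the example criterion misses Grade 2 holds that resume at the same dose.

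Third, each dosing visit already includes an examination based on symptom review. This narrows the gap to a participant whose new Grade 2 symptom is neither asked about nor volunteered. The documents give no rate for that.

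Footnote n is modest support only: it shows that the protocol allows for significant ocular events in Cycle 1, not that they are likely after limited toxicity in escalation. The timing of the ophthalmic examination does not argue for the fix either, because symptom questions would not find asymptomatic signs.

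**Conclusion.** The concern holds. Under the stated conditions, 4 of 6 Schedule B infusions in Cycles 1 and 2, and 1 of 2 in each later cycle, have no required ocular symptom assessment, and no other provision supplies one. These are scheduling counts. They do not estimate how many Grade 2 events would be missed, and nothing in the documents allows that estimate. The gap rests on all four conditions being met, the SAP's RP2D makes them less likely, and existing safeguards cover part of it. It is a low-priority improvement to participant safety with no effect on the efficacy analysis.

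**What to change.** In Protocol Section 7.2 and Appendix 2 footnote g, state that in expansion on Schedule B the ocular symptom assessment is done before each infusion: Days 1, 8 and 15 in Cycles 1 and 2, and Days 1 and 8 from Cycle 3. Keep the provision for more frequent assessment once symptoms or signs appear, and leave Schedule A expansion at Day 1. Under the reduced rule, uncovered infusions fall from 4 of 6 and 1 of 2 to zero. The change matches the Schedule B rule for physical examination and restores dosing-day marks already in the grid.

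The cost is a wording change in two places and brief questioning at visits participants already attend: 2 × 2 = 4 added assessments across Cycles 1 and 2, then one per cycle. No visits are added.
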